Study Title: LA-CEAL 4.0: Wearable Sensor Project

NCT Number

NCT06086028

Protocol Date:

11/20/2023

Study Title: Louisiana Community-Engagement Alliance (LA-CEAL) 4.0: Wearable Sensor Project

1. Study aim, background, and design

In August 2020, Louisiana (LA) ranked first in the US for COVID-19 cases by population with a case rate of 2,960 per 100,000 and fifth in deaths by population with a death rate of 97 per 100,000^{1,2}. The added strain on the healthcare system was associated with high levels of burnout and among the healthcare workforces^{3,4}.

Biofeedback is a technique in which patients use data about their own physiology to improve their mental, physical, and emotional health⁵. Biofeedback is an effective method of treating mental health symptoms and managing chronic illness. More specifically heartrate biofeedback has been successful in treating depression, anxiety, and sleep disturbances in patient populations⁶. LA-CEAL will test the value of biofeedback delivered via wearable sensor in addressing stress, burnout, depression, and anxiety in healthcare populations to enhance resilience with the long-term aim of improving workforce retention.

OBJECTIVE: To develop and test approaches for strengthening the capacity and resilience of the primary care workforce to support their roles as Trusted Messengers for Long COVID, chronic disease, preventive healthcare and clinical research participation.

This approach will use a randomized two-group crossover design to test the hypothesis that using real-time biofeedback to present, interpret, and bring attention to information regarding stress levels will increase participants readiness to change in regard to addressing burnout. To test this hypothesis, we will recruit 80 providers/staff from FQHC partner sites to participate in a 6-week crossover design. All participants will be given a wrist worn sensor developed by Biostrap. The sensor links with a phone application (API) controlled by the research team. The research team can release forms, surveys, and summary information from the wearable sensory onto the phone application. The API can also push notifications to complete self-report surveys as needed. Biostrap collects biometrics such as the following: (1) sleep pattern/ quality; (2) steps, activity, calories; (3) heart rate; (4) oxygen saturation; and (5) respiratory rate. Participants will be randomly assigned to one of two groups. The first group will receive access to their biometric data in real-time via the Biostrap API (information received condition) while the second group will be given a summary of their biometrics at the end of their 14-day control period (information delayed condition). After 1 week “washout” the conditions will cross-over, and the second group will receive real-time access to their biometrics via the Biostrap API while the first group receive their biometric report at the end of the control period. Participants will complete a pre and posttest self-report survey using the measurements tool attached.

2. Subject Population

Up to 80 participants from staff members of partner federally qualified health centers (FQHCs):

Inclusion criteria: Age >=18 years; ability to understand and speak English; staff at FQHC; smartphone compatible with the Biostrap sensor and phone application; attending work during the six week study period.

Exclusion criteria: Unable or unwilling to give informed consent, disclosed pregnancy at the start of the study, pace maker or other device regulation heart rate/rhythm, previous diagnosis of atrial fibrillation.

3. Procedure

Enrolled participants will be asked to complete 2 brief surveys via REDCap, once at the start of the study and a second time at the end, approximately 6 weeks later. The survey should take about 20-25 minutes to complete. During the six-week period, participants will be given a wearable sensor made by Biostrap. Participants will be randomly assigned to one of two groups. Both groups will be asked to wear the sensor during the six-week period. Both groups will begin with 7 days to get used to wearing the sensor. Group 1 will receive access to their biofeedback information in real-time for the next 14 days via the Biostrap dashboard on the mobile app. Group 2 will not have access to this real-time data during the same 14 day period, but will receive a summary report at the end of the 14-day period. Both groups will then have a 7-day “washout” period before switching

conditions: Group 2 will see their biofeedback information in real-time on the mobile app while Group 1 will have all real-time biofeedback information hidden, instead receiving a summary report at the end of the 14-day period. During the time participants are wearing the sensor they will receive one notification a day prompting them to answer two questions via the Biostrap dashboard. During the time they are wearing the sensor it will be recording biometric information such as: (1) sleep pattern/ quality; (2) steps, activity, calories; (3) heart rate; (4) oxygen saturation; and (5) respiratory rate. All of this data is linked with a randomly generated Study ID.

4. Risks

The risk of physical, psychological, social, or legal harm associated with participation in all components of this study is minimal:

- Though not sensitive in nature and widely used in social science research, participants may feel uncomfortable responding to some of the survey, participants will be informed that they do not have to answer any question they do not want to answer and that they can stop participating at any time without penalty.
- Participants may find it inconvenient to take time to participate in the study. All study activities will be arranged at a time that is convenient for participants.
- There is a small risk of unauthorized disclosure of participants' responses, which will be prevented by following a strict protocol for data handling and rigorous training of study staff:
 - No identifying data (e.g., name, address) will be recorded on study forms. Identifying data used for participant recruitment will be kept separate from study data and no linkage will exist.
 - All electronic study records will be stored with password-protection. All paper study records will be locked in a secure study office. Data will be accessible only by study staff with approval from the PI.
 - The data will be retained without identifiers in a secure location for possible use in a future project, which will be consistent with the original research purpose.
 - Data may be shared with the NIH or other researchers upon request. Any data shared with the NIH or other researchers will not contain identifying information.

5. Benefits

Wearable sensor project: There may not be any direct benefit from participating in the study. We have found that talking about work related stress and burnout is helpful for people. In addition, wearing a sensor like Biostrap will provide participants with information about their sleep, heartrate, activity level, and pulse oxygenation which can also help form health habits. The knowledge gained from the study may provide evidence for a strategy to improve healthcare worker well-being.

6. Remuneration

Participants will receive the following payments for completing the following study activities \$25 per week during the wearable sensor protocol (maximum of \$150 per person, \$25*6 weeks).

7. Costs

There will be no costs to the participant for participating in this research study.

8. Consent process and documentation

Eligible participants will view and sign the consent form (attached) via REDCap. Participants will review the consent form and be asked to verify their understanding of consent by Yes or No to the following statements:

- I have read this consent form, or it has been read to me.
- This study has been explained to me, including risks and possible benefits (if any) and other options besides study participation.
- I have had the opportunity to ask questions.
- I understand the information that has been provided to me.
- I have had enough time to think about participation in the study.

Participants will have the ability to click on “I consent” or “decline.” Participants will also be given the opportunity to pause the consent process to speak with a study team member to answer any questions they have.

9. References

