Study Title: LA-CEAL 4.0: Wearable Sensor Project

NCT Number

NCT06086028

Statistical Analysis Plan Date:

11/20/2023

LA-CEAL 4.0: Wearable Sensor Project Analysis Plan. Analyses for the primary outcome will test the between group differences in the percentage of days participants reported concordance between high levels of stress and engaging in a self-care activity across immediate and delayed information release arms. Secondary outcomes will test between group differences in the average levels of self-reported burnout, depression, anxiety, and resilience; as well as differences in measurements recorded via wearable sensor such as respiratory rate, activity level, sleep efficiency score, heartrate variability and heartrate (measured as beats per minute). Analyses will use both paired and independent samples t-test as appropriate. We will also test for statistically significant between groups differences in baseline characteristics.

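### On the documented survey schedule, burnout, depression, anxiety and resilience have no score under each condition, so the week-6 group test is a comparison of sequences

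*Protocol*

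**What the plan says.** Protocol section 1 describes a randomized two-group crossover in 80 staff and states: "Participants will complete a pre and posttest self-report survey using the measurements tool attached". Section 3 places the two surveys: "once at the start of the study and a second time at the end, approximately 6 weeks later".

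Section 3 also gives the sequence of conditions. After a 7-day run-in, "Group 1 will receive access to their biofeedback information in real-time for the next 14 days", while "Group 2 will not have access to this real-time data during the same 14 day period, but will receive a summary report" when those 14 days end. A 7-day washout follows and the conditions switch: Group 2 gets real-time access for 14 days, and "Group 1 will have all real-time biofeedback information hidden, instead receiving a summary report at the end of the 14-day period". Two app questions are asked each day; their content is not stated.

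Section 1 mentions one further route for self-report: "The API can also push notifications to complete self-report surveys as needed". No such survey is scheduled.

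The SAP states: "Secondary outcomes will test between group differences in the average levels of self-reported burnout, depression, anxiety, and resilience". On method it says: "Analyses will use both paired and independent samples t-test as appropriate". It does not assign either test to an outcome, and it gives no time point for the four scales and no carryover assumption.

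**The concern.** A crossover gains its precision from observing each person under both conditions. That needs a score at the end of each period, and for these four scales the schedule has none at the end of period 1. Two kinds of t-test are then left:

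- A paired start-to-end test spans both conditions plus time, so it cannot isolate real-time access.
- An independent test at week 6, on end scores or on change from start, compares people who had real-time access first with people who had it second.

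The second test is a valid randomized comparison of sequences. It becomes an estimate of the real-time effect only if what Group 1 retains from its earlier real-time access equals what Group 2 retains from its earlier delayed condition and summary report. Two surveys cannot check this.

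Protocol section 1 names burnout, depression, anxiety and resilience among the targets of the biofeedback. A null or positive week-6 result on these scales could be read as a statement about real-time feedback that the data cannot support alone.

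**Working it through.** **Timeline (Protocol section 3).** 7 + 14 + 7 + 14 = 42 days, which matches the stated six weeks. Group 1's real-time access ends on day 7 + 14 = 21. The final survey is at about day 42, so the gap is 7 + 14 = 21 days. Group 2's access ends at about day 42. Group 1's own summary report is due at the same point, and its order relative to the final survey is not stated.

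**What the week-6 difference estimates.** Let δ be the real-time effect, L the share of δ still present in Group 1 at day 42, and M Group 2's residual from period 1 as a share of δ. Period effects are common to both groups and cancel, so

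Group 2 − Group 1 at week 6 = δ(1 + M) − δL = δ(1 − L + M).

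Subtracting the start score does not change this expectation, because randomization balances start scores on average. With δ = 0.5 SD (assumed):

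| L | M | Expected week-6 difference (SD) |
|---|---|---|
| 0 | 0 | 0.50 |
| 0.25 | 0 | 0.375 |
| 0.5 | 0 | 0.25 |
| 0.5 | 0.25 | 0.375 |
| 0.25 | 0.25 | 0.50 |
| 0 | 0.25 | 0.625 |

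The difference shrinks when L > M, is unchanged when L = M, and is inflated when M > L. The documents give no value for L or M.

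**Precision.** The protocol gives 80 participants without alpha, power, effect size, SD or dropout, so there is no planned figure to reproduce. The assumptions, none of them in the documents, are 40 per group, two-sided alpha 0.05, no dropout, outcome SD 1 and equal correlation ρ between survey occasions. Calculations use the noncentral t distribution.

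- Plain end-score t-test: SE = √(2/40) = 0.224, 78 df.
- Change-score t-test: SE = √(2(1 − ρ)) × √(2/40), 78 df. At ρ = 0.6 this is 0.894 × 0.224 = 0.200.
- Start-score-adjusted comparison (ANCOVA): SE = √(1 − ρ²) × √(2/40), 77 df. At ρ = 0.6 this is 0.8 × 0.224 = 0.179.
- Within-person contrast, if period-1 scores existed: SE = √(2(1 − ρ)/80), 78 df. At ρ = 0.6 this is 0.100.

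| Analysis | Detectable at 80% power, ρ = 0.3 | ρ = 0.6 | Power at 0.50 SD, ρ = 0.6 |
|---|---|---|---|
| Plain t-test | 0.63 | 0.63 | 60% |
| Change-score t-test | 0.75 | 0.57 | 70% |
| Start-score adjusted | 0.61 | 0.51 | 79% |
| Within person | 0.38 | 0.28 | above 99% |

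At ρ = 0.3 the change score is worse than the plain t-test, while adjustment still helps. With 20% dropout (32 per group) and ρ = 0.6, the plain, adjusted and within-person values become 0.71, 0.57 and 0.32 SD.

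If carryover reduced the expected difference to 0.375 or 0.25 SD, power at ρ = 0.6 would be 38% or 20% for the plain t-test and 54% or 28% for the adjusted comparison. Adjustment improves precision but does not remove carryover.

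**The case against.** **The premise is inferred.** The measurement tool is not in the supplied text, and no section says which survey holds the four scales. The app can deliver surveys, and the SAP's reference to average levels could mean group means or averages over time. If the scales were in fact pushed in each period, the point would fall. This stands as a reason for the conditional wording. But a capability is not a schedule, and two daily questions could hardly carry four scales.

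**These are secondary outcomes, and one fewer questionnaire is defensible.** Section 5 says that talking about work stress and burnout has been found helpful, so a mid-study survey might itself influence period 2 of the primary outcome. This stands, and it is why the extra survey is offered only as an option. It is no argument against adjusting and labelling the week-6 test.

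**A reader might infer that the week-6 test is biased towards zero.** The documents do not support that. Section 5 says that sensor information may help people build healthier habits, which could apply to both groups, and Group 2 receives its own report at day 21. The bias could run either way or be absent.

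**A reader might infer that the crossover fails for the whole trial.** It does not. The daily primary outcome (apparently based on the two app questions) and the sensor outcomes are collected in both periods, so they do not share the missing-measurement problem. Their contrasts can still be affected by carryover.

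**Conclusion.** The point holds for the four self-report scales, on the documented schedule and on the inference that the scales sit only in the start and end surveys. No real-time minus delayed difference can be formed within a person for them. The available between-group test compares sequences, and it equals the real-time effect only without differential carryover, which two surveys cannot verify.

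The loss of the within-person contrast follows from the schedule alone. Its size rests on the assumptions listed: at correlation 0.6, the detectable difference is 0.63 SD for the plain t-test against 0.28 SD within person, a ratio of about 2.2 (0.63/0.28). Any carryover bias is of unknown direction and size. This should be fixed in the SAP. It does not invalidate the randomized comparison.

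**What to change.** State which survey occasions carry the four scales. Then:

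1. **In the SAP, at no data-collection cost.** Analyse the week-6 score of each scale by ANCOVA with its start score as covariate, in place of an unadjusted or change-score t-test. Do not use the paired start-to-end test as evidence of a real-time effect. Report the result as a sequence comparison that equals the feedback effect only without differential carryover. This takes a few sentences.

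2. **Optional, at small cost.** Repeat only the four scales at day 21, before Group 2's summary report, and take the final survey before Group 1's report. Use the day-21 start-score-adjusted group difference as the estimate free of period-1 carryover. Give the period-adjusted within-person contrast alongside it, noting that differential carryover can bias it. Without differential carryover, day 21 alone is no more precise than adjusted week 6; the gain in precision comes from the within-person contrast. This needs a short protocol, consent and SAP amendment and one survey, shorter than the full 20-25 minutes, through REDCap or the app.

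Option 2 has two downsides. The extra survey may draw attention to stress before period 2 of the primary outcome, possibly unequally, since the groups arrive from different conditions; the 7-day washout lies between but does not guarantee balance. And a scale whose recall window exceeds 14 days would blur the day-21 score; no recall window is given.

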Study Title: LA-CEAL 4.0: Wearable Sensor Project

NCT Number

NCT06086028

Statistical Analysis Plan Date:

11/20/2023

LA-CEAL 4.0: Wearable Sensor Project Analysis Plan. Analyses for the primary outcome will test the between group differences in the percentage of days participants reported concordance between high levels of stress and engaging in a self-care activity across immediate and delayed information release arms. Secondary outcomes will test between group differences in the average levels of self-reported burnout, depression, anxiety, and resilience; as well as differences in measurements recorded via wearable sensor such as respiratory rate, activity level, sleep efficiency score, heartrate variability and heartrate (measured as beats per minute). Analyses will use both paired and independent samples t-test as appropriate. We will also test for statistically significant between groups differences in baseline characteristics.

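### The four survey scales are to be compared between groups by t-test only; ANCOVA on the start score already planned would make that comparison of sequence groups more precise at almost no cost

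*SAP*

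**What the plan says.** The SAP's secondary outcomes include tests of "between group differences in the average levels of self-reported burnout, depression, anxiety, and resilience". On method it says only "Analyses will use both paired and independent samples t-test as appropriate". It does not say which test goes with which outcome, or whether end scores or changes are compared. Neither document mentions ANCOVA, regression, a mixed model or any covariate.

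Protocol section 1 states "Participants will complete a pre and posttest self-report survey using the measurements tool attached", and section 3 (Procedure) has participants "complete 2 brief surveys via REDCap, once at the start of the study and a second time at the end", about six weeks apart. No survey is described between the two 14-day conditions. The tool itself is not shown, so it is an assumption that it holds all four scales. Section 2 sets the sample at "Up to 80 participants from staff members of partner federally qualified health centers".

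**The concern.** With two survey points and a between-group aim, the named method that fits is the independent t-test, on end scores or on changes. The first ignores the start score. The second gives it a fixed weight of one, whatever the correlation between start and end. ANCOVA estimates that weight from the data.

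Only precision is at stake. The sample is capped at 80, so precision cannot easily be bought with more recruitment, whereas the start score is already due to be collected.

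**Working it through.** The documents give no alpha, power, SD, correlation, allocation ratio, dropout or sample-size calculation, so there is no planned figure to reproduce.

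**Inputs.** From the documents: N = 80 (a maximum), two randomized groups, surveys at start and end. Assumed: 40 per group, two-sided 5%, 80% power, the same SD at start and end (set to 1), and start-end correlation r of 0.3, 0.5 or 0.7.

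**Variance of the group difference, relative to the end-score t-test.**
- End score: 1.
- Change score: 2(1 − r) = 1.40, 1.00, 0.60.
- ANCOVA: (1 − r²) × (N − 3)/(N − 4). The second factor is the expected cost of estimating the slope, 77/76 = 1.0132. This gives 0.91 × 1.0132 = 0.922, 0.75 × 1.0132 = 0.760 and 0.51 × 1.0132 = 0.517.

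A simulation of 20,000 trials per correlation gave ANCOVA ratios of 0.920, 0.759 and 0.520, in agreement with the formula.

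**Detectable difference and power.** The standard error is √(2/40) = 0.224 SD times the square root of the variance factor. Noncentral t was used, with 78 degrees of freedom for the t-tests and 77 for ANCOVA. Power is for an assumed true difference of 0.5 SD.

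| | r = 0.3 | r = 0.5 | r = 0.7 |
|---|---|---|---|
| Detectable, end score (SD) | 0.634 | 0.634 | 0.634 |
| Detectable, change score (SD) | 0.751 | 0.634 | 0.491 |
| Detectable, ANCOVA (SD) | 0.609 | 0.553 | 0.456 |
| Power, end score | 60% | 60% | 60% |
| Power, change score | 46% | 60% | 81% |
| Power, ANCOVA | 63% | 72% | 87% |

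**Sample size that each t-test would need to match ANCOVA with 80.**
- End score: 80/0.922, 80/0.760 and 80/0.517, or about 87, 105 and 155.
- Change score: 80 × 2/[(1 + r) × 1.0132], or about 121, 105 and 93.

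The fair comparator is the better t-test at each correlation: the end score at 0.3, either at 0.5, and the change score at 0.7. Against it, 80 people under ANCOVA are worth about 87, 105 and 93.

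**Break-even.** ANCOVA matches the end-score t-test when 1 − r² = 76/77, that is r = √(1/77) = 0.114. Below that it loses, by at most 1.3% of variance.

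**Smaller sample.** At an assumed 32 per group the slope factor is 61/60 = 1.0167 and the break-even correlation is √(1/61) = 0.128. The detectable difference is 0.71 SD for end scores; 0.84, 0.71 and 0.55 SD for change scores; and 0.68, 0.62 and 0.51 SD for ANCOVA. The pattern is the same.

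**Why within-participant contrasts are left out.** Adjusting a period difference for one baseline taken before period 1 cuts its variance by (r01 − r02)²/[2(1 − r12)]. Here r01 and r02 are the baseline's correlations with periods 1 and 2, and r12 is the correlation between the periods. With r01/r02/r12 of 0.5/0.5/0.5, 0.5/0.4/0.5 and 0.5/0.3/0.5 the cut is 0%, 1% and 4%. With 0.7/0.5/0.7 it is 6.7%. The participant already serves as their own control, so there is little left to gain.

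**The case against.** The strongest objection is that this sharpens a contrast that answers none of the trial's stated questions. The hypothesis in protocol section 1 concerns real-time biofeedback, and the end survey comes after both groups have had it. A group difference at that point reflects order of conditions, and no order hypothesis is stated. The 0.5 SD used for power has no basis in the documents. At an assumed 0.2 SD, end-score power is 14% and ANCOVA power is 15%, 17% or 23%, all inadequate. This stands as a limit on the value of the point. It does not make the less precise test preferable, because the SAP still commits to the between-group test.

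A second objection is that the SAP leaves the choice of t-test open, so a change-score test fits its text as well as an end-score test. That is right, and it is why the gain has to be judged against the better of the two. The open wording does not otherwise settle the matter: a paired start-to-end test does not compare groups, and neither independent t-test is as precise as ANCOVA at the correlations examined.

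A third is that every figure depends on an assumed correlation. That also stands. The documents do not narrow the range.

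**Conclusion.** The point holds as a low-cost improvement to a secondary analysis. It is not an error in the plan. Against the better t-test at 40 per group, ANCOVA lowers the detectable difference from 0.634 to 0.609 SD at correlation 0.3, from 0.634 to 0.553 SD at 0.5, and from 0.491 to 0.456 SD at 0.7. These figures rest on the assumed correlation, equal SDs, equal allocation and full retention of 80, and on the unseen tool containing the four scales.

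A reader might infer three stronger things that the documents do not support:
- **That the planned t-test is biased or invalid.** Under randomization it is neither, and its standard error already allows for chance imbalance at the start.
- **That adjustment would recover the effect of real-time feedback on these scales.** It cannot, because both groups have had both conditions by the end survey.
- **That ANCOVA is worth nearly a doubling of the sample at high correlation.** The figure of about 155 at 0.7 holds only against an end-score t-test. Against a change-score t-test it is about 93.

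The primary outcome (daily concordance of high stress with self-care), paired tests and contrasts of period differences are unaffected.

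**What to change.** In the SAP, for burnout, depression, anxiety and resilience:
- Replace the independent t-test with ANCOVA of the end score on randomized group and the participant's own start score on the same scale.
- State the rule for a missing start score.
- State that the comparison is between sequence groups and does not estimate real-time against delayed feedback.

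Leave the paired and period-difference contrasts without this adjustment.

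The cost is SAP wording, one degree of freedom per model and about 1.3% of variance for estimating the slope. ANCOVA would lose to the end-score t-test only if the start-end correlation were below about 0.11. No new data, visits or participants are needed. Naming one model in advance also removes the unstated choice between end and change scores.
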